9.8 Efficacy Analyses

Due to observations related to safety, the study was terminated by the sponsor prior to completion. The sample size at the time of study termination does not support formal comparisons of the treatment groups, and therefore, no efficacy analyses specified in the protocol will be performed. Descriptive statistics for efficacy endpoints will be provided as described below.

Furthermore, no patient reached their Week 12 visit, and therefore, descriptive statistics at Week 12 will not be presented. Instead, descriptive statistics will be provided for all analysis visits up to the last non-missing visit.

9.8.1 Primary Efficacy Analysis

The primary endpoint is used to evaluate the primary objective of assessing the efficacy of each of the 2 miricorilant doses (600 mg and 900 mg) compared with placebo in reducing liver fat content. More specifically, each dose of miricorilant will be compared with placebo on the

relative change from baseline in LFC assessed by MRI-PDFF, where for the l^{th} patient, the relative change is calculated as

$$Z_{x,l} = ((LFC_{x,l} - LFC_{bl})/LFC_{bl}) \times 100$$

where $LFC_{x,l}$ is the LFC measured at visit x for the l^{th} patient, and LFC_{bl} is the baseline LFC for the l^{th} patient.

Descriptive statistics (mean, standard deviation, median, 25th and 75th percentiles, minimum, and maximum) will summarize the relative change from baseline to post-baseline in LFC by treatment group and overall.

9.8.1.1 Sensitivity Analyses

No sensitivity analyses will be performed.

9.8.2 Secondary Efficacy Analyses

9.8.2.1 Relative Change from Baseline in Liver Fat Content for Both Dose Levels of Miricorilant Combined vs Placebo

For the first secondary endpoint, the 2 miricorilant dose groups will be combined into a single treatment group and descriptive statistics will summarize the relative change from baseline to post-baseline in LFC by treatment group.

9.8.2.2 Responders Achieving a $\geq 30\%$ Reduction in Liver Fat Content

The second secondary efficacy endpoint is the percentage of patients achieving a $\geq 30\%$ reduction in the relative change in LFC from Baseline for each of the 2 miricorilant doses versus placebo. The endpoint requires calculation of the relative change in LFC as described in [Section 9.8.1](#).

The outcome variable will be a binary variable indicating a patient as a responder, that is whether the l^{th} patient achieved a $\geq 30\%$ reduction in LFC from baseline:

$$\theta_l = \begin{cases} 1 & \text{if } Z_{x,l} \leq -30 \\ 0 & \text{otherwise} \end{cases}.$$

where $Z_{x,l}$ is the relative change in LFC ([Section 9.8.1](#)).

A frequency table for the number of patients who have achieved a $\geq 30\%$ reduction in LFC from baseline to post-baseline will be provided.

9.8.2.3 Absolute Change from Baseline in Liver Fat Content

Descriptive statistics will summarize the absolute (arithmetic) change from baseline in LFC by treatment group and overall post-baseline.

9.8.2.4 NASH Biomarkers

9.8.2.4.1 AST, ALT, and GGT

Separate from laboratory summaries, descriptive statistics will summarize AST, ALT, and GGT by treatment and overall at all non-missing corresponding visits associated with NASH Biomarker data collection. The change from baseline in AST, ALT, and GGT will be presented by treatment and overall at all non-missing post-baseline analysis visits.

9.8.2.4.2 Propeptide of Type III Collagen (pro-C3)

Small fragments of collagen, called propeptides, are released during fibrosis. Pro-C3 is the propeptide of type III collagen and detection of pro-C3 is anticipated to reflect the formation of new fibrotic tissue in the liver ([Vilar-Gomez and Chalasani 2018](#)).

Descriptive statistics will summarize pro-C3 by treatment and overall at all non-missing visits and the change from baseline in pro-C3 by treatment and overall at all non-missing post-baseline analysis visits.

9.8.2.4.3 Enhanced Liver Fibrosis (ELF) Score and Its Components

The ELF score combines 3 serum biomarkers (hyaluronic acid, TIMP-1, and PIIINP) which have been shown to correlate with the degree of liver fibrosis assessed by liver biopsy ([Vilar-Gomez and Chalasani 2018](#)). Each of these markers is measured by an immunoassay and an ELF score is generated, from which a level of fibrosis severity can be determined.

Descriptive statistics will summarize the ELF score and its components by treatment and overall at all non-missing visits and the change from baseline in the ELF score and its components by treatment and overall at all non-missing post-baseline analysis visits.

9.8.3 Exploratory Analyses

9.8.3.1 Responders Achieving a $\geq 50\%$ Reduction in Liver Fat Content

The percentage of patients achieving a $\geq 50\%$ reduction in the relative change in LFC from baseline for each of the 2 miricorilant doses versus placebo will be determined as described in [Section 9.8.2.2](#). A frequency table for the number of patients who have achieved a $\geq 50\%$ reduction in LFC from baseline to post-baseline will be provided.

9.8.3.2 Proportion of Patients with Complete Resolution

Complete resolution of fatty liver is any MRI-PDFF value less than 5%. A frequency table for the number of patients who have achieved complete resolution in LFC from baseline to post-baseline will be provided. Patients with complete resolution of fatty liver by MRI-PDFF will be listed including duration on study drug, last dose date, MRI date, and duration between last dose date and MRI date.

9.8.3.3 Homeostatic Model Assessment for Insulin Resistance

HOMA-IR will be calculated by the central laboratory for each patient at each visit using the approximate formula ([Matthews et al. 1985](#)):

$$\text{HOMA-IR} = (\text{glucose (mg/dL)} \times \text{insulin (\mu U/mL)})/405.$$

Descriptive statistics will summarize HOMA-IR by treatment group and overall for all visits and the change and percent change from baseline in HOMA-IR by treatment group and overall for all post-baseline analysis visit.

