 - b. Have had an insulin dose adjustment >10% within 60 days prior to enrollment
 - c. Have a requirement for glucagon-like peptide analogue (unless on a stable dose ≥ 3 months prior to Screening), a requirement for sodium/glucose cotransporter 2 (SGLT2) inhibitors (unless on a stable dose ≥ 3 months prior to Screening), or 3 or more oral anti-diabetic (OAD) agents (unless the OAD is stable and HbA1c <8%)

- d. Have a history of severe hypoglycemia (symptomatic hypoglycemia requiring outside assistance to regain neurologic status)
- 15. Are currently taking a statin other than stable doses of the following: lovastatin (up to 20 mg), pravastatin, pitavastatin, simvastatin (up to 10 mg), atorvastatin (up to 20 mg), or fluvastatin (up to 20 mg). A stable dose is defined as no changes in the dose in the last 3 months prior to Screening.
- 16. Are currently on the oral antidiabetic drug nateglinide (Starlix).

Patients currently taking the medication may participate in the study if it is appropriate to discontinue the medication, and if the patient is amenable to discontinuing the medication for a wash out period of 5 half-lives prior to the baseline assessment.

- 17. Are currently using a medication such as digoxin with an increased risk for toxicity in the event of electrolyte changes.
- 18. Have weight loss of greater than 10% within the last 6 months prior to Screening.
- 19. Have abnormal screening laboratories:
 - a. AST $>5\times$ upper limit of normal (ULN)
 - b. ALT $>5\times$ ULN
 - c. Estimated glomerular filtration rate (eGFR) ≤ 60 mL/min/1.73 m²
 - d. Creatine kinase $>3\times$ ULN
- 20. Have known or suspected cirrhosis based on the opinion of the Investigator. The list below represents possible signs of suspected cirrhosis:
 - a. Physical exam findings:
 - i. Jaundice
 - b. Laboratory findings
 - i. Direct bilirubin >0.3 (except for patients who have Gilbert's syndrome; see exclusion criterion #21f)
 - ii. Platelet count $<140,000/\mu\text{L}$
 - c. Imaging:
 - i. Evidence of portal hypertension (dilated portal vein, presence of varices)
 - ii. Evidence of a nodular liver with splenomegaly
 - d. Endoscopy:
 - i. Evidence of esophageal varices
- 21. Have hepatic decompensation defined as the presence of any of the following:
 - a. Serum albumin <3.5 g/dL
 - b. International normalized ratio (INR) >1.3 (unless due to therapeutic anticoagulants)

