5.4.1 Permitted Concomitant Medications

Medications required to treat AEs, manage symptoms, concurrent diseases, and supportive care agents, such as pain medications, anti-emetics, and antidiarrheal agents, are allowed at the discretion of the Investigator and/or the Corcept Medical Monitor. Patients must be instructed to notify the investigational site about any new medications they take after the start of the study drug. All medications (other than study drugs) administered 28 days before study entry (i.e., after a patient signs the ICF) and during the study must be listed on the concomitant medications eCRF.

Permitted concomitant medications are listed in [Table 3](#).

Table 3 Permitted Concomitant Medications

Medication	Use and/or Restriction
Insulin and oral antidiabetic medication	Dose can be decreased during treatment with study drug to prevent hypoglycemia; upward titration should be avoided and may occur only after consultation with the Corcept Medical Monitor.
Antihypertensive medication	Dose can be decreased during the treatment with study drug to prevent hypotension or orthostatic symptoms. Do not increase dose or add new antihypertensive medications without prior consultation with the Corcept Medical Monitor.
Lipid-modifying drug	No changes in current dose allowed from 6 weeks before Baseline through the Follow-up Visit. Do not add new lipid-modifying medications without prior consultation with the Corcept Medical Monitor.

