3.3 Exploratory Objectives

- To be assessed by patient group:
 - In all patients, change in adrenocorticotropic hormone (ACTH), serum cortisol, serum aldosterone, absolute body weight, and insulin resistance.
 - In patients with diabetes, change in glycated hemoglobin (HbA1c) and fasting blood glucose.
 - In patients with high blood pressure, change in blood pressure.
- To evaluate the dose-response relationship between miricorilant and change in liver fat content.

- To evaluate the exposure-response relationship between miricorilant and change in liver fat content.

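### HOMA-IR is summarised for all patients, including any on insulin, in whom the measured insulin may include injected drug and the index may not measure insulin resistance

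*SAP*

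**What the plan says.** The SAP's exploratory objective (3.3) covers every patient: "In all patients, change in adrenocorticotropic hormone (ACTH), serum cortisol, serum aldosterone, absolute body weight, and insulin resistance". SAP 4.3 likewise puts HOMA-IR among the all-patient endpoints. For the calculation, SAP 9.8.3.3 says "HOMA-IR will be calculated by the central laboratory for each patient at each visit using the approximate formula": glucose in mg/dL times insulin in µU/mL, divided by 405. Descriptive statistics follow for the values and for "the change and percent change from baseline in HOMA-IR by treatment group and overall for all post-baseline analysis visit". The section has no rule for patients on insulin.

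The protocol admits such patients. Within type 2 diabetes, exclusion 14b (section 4.2) removes only those who "Have had an insulin dose adjustment >10% within 60 days prior to enrollment". In Table 3 (section 5.4.1), "Insulin and oral antidiabetic medication" is a permitted category with this restriction: "Dose can be decreased during treatment with study drug to prevent hypoglycemia; upward titration should be avoided". An increase is possible only after the Medical Monitor has been consulted.

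**The concern.** HOMA-IR is read as a measure of insulin resistance on the understanding that fasting insulin is what the patient's own pancreas secretes. In a patient who injects insulin, the measured value may be partly or wholly the injected drug. If the assay does not detect the product used, the value may instead leave that drug out. Either way the product of glucose and insulin need not track resistance, and a change in it may reflect a change in prescription.

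The plan pools these values with the interpretable ones. Randomisation is stratified by diabetes (Protocol 5.5), not by insulin use, so chance may place insulin users unevenly across arms. The sample at termination was too small for formal comparisons (SAP 9.8), and in small arms a few such patients could weigh noticeably on a mean change or mean percent change. SAP 9.8.3.7 drops the diabetes-specific HbA1c and glucose analyses, so HOMA-IR is the only glycaemic measure left in the SAP's efficacy section.

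**Working it through.** The plan states no figure to reproduce here. The check has two parts.

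**1. Do the documents let injected insulin into the summary, and does anything separate it?**

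- Eligibility: insulin-treated type 2 diabetes is allowed if the recent dose was stable (Protocol 4.2, 14b).
- Continued use: permitted (Protocol Table 3).
- Measurement: Protocol Table 5 lists fasting serum insulin. It lists no C-peptide, and neither document states assay specificity, so the planned data cannot separate secreted from injected insulin.
- Analysis set: every patient with a value (SAP 9.8.3.3).
- Separate summaries: none. SAP 9.8.3.7 drops analyses in patients with diabetes, and SAP 9.10 plans no subgroups.

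So the values enter the arm summaries, and no planned table shows the result without them.

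**2. What would an insulin dose reduction do to the index?**

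Let c be the fractional dose cut, s the share of measured insulin that is injected, and g the fractional change in fasting glucose. Measured insulin is multiplied by 1 − cs. Because the SAP formula is a product,

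relative change in HOMA-IR = (1 − cs)(1 + g) − 1,

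which is zero when g = 1/(1 − cs) − 1.

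The documents give none of c, s or g. As an assumption, take c = 20%, with s at 0 (assay misses the product), 50% and 100%:

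| Injected share seen by assay | Measured insulin | g = 0 | g = +10% | g = +20% | g = +30% | Break-even g |
|---|---|---|---|---|---|---|
| 0 | unchanged | 0% | +10% | +20% | +30% | 0% |
| 50% | −10% | −10% | −1% | +8% | +17% | 11.1% |
| 100% | −20% | −20% | −12% | −4% | +4% | 25.0% |

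Example, second row: 0.90 × 1.20 − 1 = +8%, and 1/0.90 − 1 = 11.1%.

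The same dose cut can lower HOMA-IR, leave it almost unchanged or raise it. The sign depends on the assay and on the glucose response. The g = 0 column should not be read as the size of an artefact: a patient who holds the same fasting glucose on less insulin may really have become less resistant. The table shows only that the index moves with the prescription, and that the documents do not fix which way.

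**The case against.** The strongest case for leaving the plan alone is that little depends on this table. HOMA-IR is exploratory. The study was stopped early for safety, no patient reached Week 12, and SAP 9.8 rules out the efficacy analyses specified in the protocol. Medians and quartiles are planned beside means (SAP 7.2 and 9.1), which limits the pull of one or two patients. Laboratory values and medications will be listed by patient (SAP 9.9.3 and 9.6), so a careful reader could find the insulin users. There may be none.

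This stands as a limit on importance. It does not make the pooled summary valid for insulin users, and assembling the correct set from separate listings is work that the SAP can do in one clause.

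A reader might go further and infer from Table 3 that dose cuts will show up as improved insulin resistance and so favour the active arms. The documents do not support that. Cuts made to prevent hypoglycaemia may well accompany low or falling glucose, which makes a fall in HOMA-IR plausible. But a glucose rise can cancel or reverse it, and if the assay misses the injected product, a cut does not directly lower the measured value. Table 3 applies equally to all three arms under double-blinding. A difference between arms would need study drug to change glucose or insulin requirements, which would itself be a metabolic effect. Increases are also not forbidden, since they may follow consultation.

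**Conclusion.** The point holds as one of validity, not of directional bias. The HOMA-IR summary by arm may include patients in whom the index does not measure insulin resistance, and on-study insulin changes may shift their values. The direction and size of any effect on the arm summaries cannot be determined from the documents. The conclusion assumes that at least one randomised patient used insulin and that the assay either registers some injected insulin or misses an analogue; the documents settle neither. The consequence is limited to one descriptive exploratory table, so the point is minor and worth making because the remedy is cheap.

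**What to change.** In SAP 9.8.3.3:

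- Summarise HOMA-IR, with change and percent change, in patients not receiving insulin at baseline. Keep the all-patient summary as supportive if wanted.
- List baseline insulin users' glucose, insulin and HOMA-IR by visit in a separate listing.
- Flag any insulin start or dose change on study in the listing. Do not remove patients from the summary for it: that would select on a post-randomisation event that treatment may affect.

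Concomitant medications are recorded at every visit (Protocol Appendix A) and coded to ATC level 4 (SAP 9.6), so baseline users can be identified without new data. The dose-change flag assumes that the dose reaches the database. Protocol 5.7 asks patients to note doses in the diary, but the documents do not say that the medication eCRF captures them.

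The cost is fewer patients in one exploratory table and a departure from the all-patient wording of SAP 3.3 and 4.3. That departure should be recorded in SAP section 10, or in the clinical study report if the SAP is already final. No change to the protocol's insulin rules is implied.

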9.8.3.4 Adrenocorticotrophic Hormone

ACTH will be listed by patient and visit including change from baseline.

9.8.3.5 Serum Cortisol

Like ACTH, serum cortisol will be listed by patient and visit including change from baseline.

9.8.3.6 Serum Aldosterone

Serum aldosterone will be summarized by descriptive statistics including change from baseline for all analysis visits during the treatment and follow-up period.

9.8.3.7 Other Exploratory Analyses in Patients with Diabetes or High Blood Pressure

No analyses will be performed for patients with diabetes or high blood pressure.

9.9 Safety Analyses

All safety analyses will be performed in the Safety Population. All safety data will appear in by-patient data listings. Unless specified otherwise, the categorical safety analyses will include both scheduled and unscheduled visits. No comparisons between treatment groups for safety measures will be made.

9.9.1 Adverse Events

TEAEs are defined as those AEs with onset on or after the first dose date of study drug or existing events that worsened after the first dose during the study and up to and including 28 days after the last dose of study drug, per protocol. Any AEs reported more than 28 days after the last dose of study drug will be considered post-treatment AEs.

Events reported with a partial onset date (e.g., month and year are reported but the day is missing) will be considered to be treatment-emergent, as appropriate, if it cannot be confirmed that the event onset was prior to the first dose of study drug based on the available date entries.

Summaries that are displayed by system organ class (SOC) and preferred terms (PT) will be ordered by alphabetical order of SOC and by descending total incidence PT nested within each system organ class. Summaries displayed by PT only will be ordered by descending total incidence of PT.

Tabular summaries with numbers and percentages of patients that have the following adverse events will be provided:

- Overview of TEAEs
- Summary of TEAEs
- Summary of TEAEs related to study drug (defined as possibly related, probably related, or related)
- Summary of TEAEs leading to discontinuation
- Summary of Serious TEAEs
- Summary of Serious TEAEs related to study drug
- Summary of Serious TEAEs leading to discontinuation
- Summary of TEAEs with fatal outcome
- Summary of TEAEs with Grade 3 or higher

All above summaries will be presented by PT, and by PT nested within SOC. Also, summaries by maximum severity will be provided for TEAEs and Serious TEAEs.

All AEs, whether treatment-emergent or not, will be listed by treatment arm and individual patient, including dates of onset and resolution and associated study day, duration, serious, NCI-CTCAE grade (CTCAE v.5.0), action taken, outcome, and relationship to study drug. Serious TEAEs and TEAEs leading to discontinuation will also be listed separately.

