4.4 Safety Endpoints

The following endpoints will be assessed for miricorilant versus placebo:

- Incidence of treatment-emergent adverse events (TEAEs), adverse events (AEs), and Serious TEAEs.
- Changes from Baseline in clinical laboratory tests (hematology and chemistry panels).
- Changes from Baseline in physical examinations and vital sign measurements.
- Changes from Baseline in electrocardiogram (ECG) parameters.

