9 STATISTICAL METHODS

9.1 General Statistical Consideration

Statistical analyses will be reported with tables, figures, and listings, presented in rich text format, and using recommended ICH numbering. Output specifications for all tables, figures, and listings will be in conformance with guidelines specified by the [ICH of the Electronic Common Technical Document Specification](#) (Apr 2003).

All summaries will be presented by assigned treatment group, or actual treatment group where applicable. In addition, data will be tabulated for all patients combined. All relevant data collected on the electronic case report form (eCRF) will be presented in by-patient data listings, to include the site identifier, patient number, and assigned treatment group.

In general, continuous variables will be summarized by the number of patients with non-missing data, mean, SD, median, 25th percentile, 75th percentile, minimum, and maximum values. Categorical variables will be summarized by the number and percentage of patients in each category.

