9.7 Extent of Exposure and Study Drug Compliance

All recorded information on oral dosing of miricorilant, including kit number, actual dose, start and end date, any dose modifications and related reason will be presented in a data listing sorted by start date of administration.

A table by treatment arm and overall will provide summary statistics on the following:

- Duration of Exposure: The duration of exposure for each study drug will be presented in days and calculated as:

$$\text{Duration} = \text{Expected date of last dose} - \text{Date of the first dose} + 1.$$

Expected date of last dose will be the latest of either the last dose date or the last missed dose date.

- Total Tablets Received: The total dose received for each study drug will be:

$$\text{Total Tablets Received} = \text{Total tablets dispensed} - \text{Total tablets returned}.$$

- Total Tablets Expected: A patient will have an expected number of tablets determined by the earliest start date and the latest end date times six tablets taken daily. For patients where their tablets received is either zero or missing, an associated expected number of tablets is included in the total tablets expected derivation. Therefore, the total tablets expected to be taken is:

$$\text{Total Tablets Expected} = \text{Duration of Exposure} \times 6.$$

- Compliance: Compliance is calculated for each study drug as:

$$\text{Compliance} = (\text{Total Tablets Received} / \text{Total Tablets Expected}) \times 100.$$

A by-patient listing including the study drug start date, study drug end date, duration, number of pills taken, number of pills expected to be taken, and overall compliance will be produced.

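### TEAE tables carry only crude percentages, although the trial was stopped early for safety and time at risk varies by patient and may differ by arm; descriptive exposure-adjusted rates and a pooled miricorilant column should be added

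*SAP*

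**What the plan says.** SAP 9.8 records that "Due to observations related to safety, the study was terminated by the sponsor prior to completion" and that "no patient reached their Week 12 visit". Formal efficacy comparisons were dropped, and SAP 10 removes the PK analysis, so safety is the main output left.

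For adverse events, SAP 9.9.1 states: "Tabular summaries with numbers and percentages of patients that have the following adverse events will be provided". This covers every TEAE table: any, related, leading to discontinuation, serious, fatal, and Grade 3 or higher. An event counts as treatment-emergent from first dose "up to and including 28 days after the last dose of study drug, per protocol"; SAP 7.1 defines the same window.

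Exposure is handled separately. SAP 9.7 says: "A table by treatment arm and overall will provide summary statistics on the following", and duration of exposure is one of the items. Onset dates and study days appear only in the AE listings.

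On columns, SAP 9.1 gives summaries by treatment group and adds: "In addition, data will be tabulated for all patients combined". SAP 9.8.2.1 pools the two miricorilant doses, but only for liver fat. SAP 4.4 introduces the safety endpoints with "The following endpoints will be assessed for miricorilant versus placebo", whereas SAP 9.9 says that treatment groups will not be compared on safety.

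**The concern.** A crude percentage can be read across arms only if the arms were at risk for similar lengths of time. Here that cannot be taken for granted. Follow-up was cut short, the end of each patient's risk window depends on when that patient stopped drug, and Protocol 5.3.3 (Table 2) contains stopping criteria triggered by toxicity. If those criteria were met more often on miricorilant, its patients would have fewer days in which to show any other event.

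The SAP was written after the termination was known. It changed the efficacy and PK sections to suit but left the TEAE measure as it would be for a trial with a fixed 12-week course.

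The column layout is a lesser gap. Safety is framed as drug against placebo, yet no safety column shows the two doses together. The only pooled column includes placebo.

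**Working it through.** The plan states no adverse event rate, no exposure by arm and no sample size at termination. There is therefore no figure to reproduce, and every rate and duration below is an assumption.

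**1. Same true rate, different time on drug.** Let p be the risk per 28 days, constant over time, and d the days on drug. The 28-day tail comes from SAP 7.1.

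Crude percentage = 1 − (1 − p)^((d + 28)/28)

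For p = 10%: d = 56 gives 1 − 0.9³ = 27.1%, and d = 28 gives 1 − 0.9² = 19.0%. The ratio is 0.70 where the true ratio is 1.

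| p per 28 days | 56 vs 28 days | 70 vs 14 days | 42 vs 35 days |
|---|---|---|---|
| 5% | 14.3% vs 9.8% (0.68) | 16.4% vs 7.4% (0.45) | 12.0% vs 10.9% (0.91) |
| 10% | 27.1% vs 19.0% (0.70) | 30.8% vs 14.6% (0.47) | 23.2% vs 21.1% (0.91) |
| 30% | 65.7% vs 51.0% (0.78) | 71.3% vs 41.4% (0.58) | 59.0% vs 55.2% (0.94) |

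Without the tail, 56 vs 28 days would give ratios of 0.51 to 0.59. The 28-day window softens the effect but does not remove it.

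**2. Staggered truncation.** This simulation lets the sponsor's stop fall uniformly between days 7 and 77 on drug, with a 10% placebo risk per 28 days. The active arm stops at half that time for a reason unrelated to the event being counted.

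- Equal true rates: crude 16.8% vs 22.9%, ratio 0.73; exposure-adjusted ratio 1.00.
- True rate ratio 2: crude 30.6% vs 23.0%, ratio 1.33; exposure-adjusted ratio 1.99.

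**3. When the event itself causes the stop.** With the same set-up and equal rates, but active patients stopping at the event, the crude figures are 23.0% vs 22.9%, although mean exposure is 38 vs 42 days. The event is already counted, so there is no distortion.

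**4. Does the adjusted rate survive off-drug dilution?** Take placebo at 0.05 per week over 14 weeks at risk. Take the active arm at 0.075 per week for 5 weeks on drug, then 0.05 for the 4-week tail.

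- Crude placebo: 1 − exp(−0.05 × 14) = 0.503.
- Crude active: 1 − exp(−0.075 × 5 − 0.05 × 4) = 0.437. The crude ratio is 0.437/0.503 = 0.87.
- Active patient-time to first event: (1 − e^(−0.375))/0.075 + e^(−0.375)(1 − e^(−0.2))/0.05 = 4.17 + 2.49 = 6.66 weeks.
- Active rate: 0.4373/6.661 = 0.0657 per week. The rate ratio is 0.0657/0.05 = 1.31.

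The on-drug ratio is 1.5. The adjusted figure falls short of it but points the right way; the crude figure does not.

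**5. Columns.** At 1:1:1 allocation with assumed rates of 10% on placebo and 30% in each miricorilant arm, the all-patients column shows (10 + 30 + 30)/3 = 23.3%. Pooled miricorilant is 30%.

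**The case against.** The strongest reply is that nothing in the documents shows unequal exposure. Randomisation was 1:1:1, and a sponsor stop truncates every arm alike. Imbalance would need differential discontinuation, which no section reports. This stands. A reader might infer that the active arms were exposed for less time and are therefore made to look safer than they are; the documents do not support that inference.

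A reader might also infer that crude percentages hide the toxicity that ended treatment. Step 3 shows that they do not. Any understatement is limited to other events that could still have occurred.

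The SAP rules out between-group safety comparisons, tabulates exposure by arm, lists every event with its onset day, and adds an eDISH plot and liver-abnormality tables (SAP 9.9.3). For a small terminated study this is a reasonable base. But the exposure table can reveal an imbalance without adjusting any percentage for it. Arm columns printed side by side will be compared whatever the text says.

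Finally, the all-patients column is not an error. It is additional to the arm columns and plainly labelled, and a reader can pool the two doses by adding their counts. Calling it misleading would go too far. What is missing is a miricorilant-combined column.

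**Conclusion.** The concern holds as a conditional one. SAP 9.9.1 offers crude numbers and percentages only, in a trial where time at risk depends on each patient's last dose and may differ by arm. If active patients stopped sooner, crude percentages can understate their rate of events other than those that caused the stop.

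The size depends wholly on exposure figures that the documents do not give. It is nil if exposure was similar. Assuming equal constant hazards and 28-day risks of 5% to 30%, it is a relative understatement of about 6% to 9% at 42 vs 35 days, and about 22% to 32% at 56 vs 28 days. The missing pooled column is a gap in display, not a bias. Together they justify a cheap improvement to the safety tables; they do not invalidate the safety analysis.

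**What to change.** Keep the crude percentages and the all-patients column. For five categories (any TEAE, related, Grade 3 or higher, serious, leading to discontinuation), and not for every preferred-term or system-organ-class row, add by arm and for a new miricorilant-combined column:

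- patients with a first event, n;
- patient-time, the sum of tᵢ in weeks;
- the rate per 100 patient-weeks, 100 × n / Σtᵢ.

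Define tᵢ as the time from first dose to the earliest of the first event in that category, 28 days after the actual last dose, or end of follow-up. Do not reuse the SAP 9.7 duration, which can run to the last missed dose and omits the 28-day tail. Label the rates descriptive, which is consistent with SAP 9.9. If the SAP is not reopened, record the addition in the clinical study report, as SAP 1 requires for departures from the plan.

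The cost is a few lines of SAP text and one patient-time derivation per category, from dates already collected. The downsides are wider tables, imprecise rates at small numbers, a constant-rate assumption, and some dilution from the 28 off-drug days (1.31 against 1.5 in the example above). Those are reasons to show the rates beside the percentages and not in place of them.
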